Patients lists (aged 70 or older and on 5 or more medications) residing at each of the LTC facility will be generated by administrative staff. The study team will work with the LTC facility to develop a consent process. This process will include verbally reviewing expectations of participation, written consent, and confirming inclusion criteria. For those who are unable to provide written consent, consent will be sought by the substitute decision maker. We will provide information evenings for families of all residents considering participation.

Intervention

The intervention as a structured medication review through integrated consultations with a pharmacist and then a physician. The review is based on patient (or family where appropriate) preferences and priorities for treatment and available evidence. A 'pause and monitor' plan for medications suitable for discontinuation or dose reduction is developed, including agreed criteria for monitoring and for restarting medications (**see Figure 1 for TAPER diagram**). Key aspects of the intervention include:

1. **Resources, evidence and guidance to support medication discontinuation.** A systematic review of potentially useful tools has been completed and an eHealth platform (TAPERMD) developed for automatic detection of ADEs and screening for potentially inappropriate medications. It combines the Beers List, STOPP criteria, Anticholinergic Burden, hypotension burden, serotonin burden, QT burden and an interaction checker as well as deprescribing guidelines and evidence for benefits in older adults.
2. **Formal incorporation of patient priorities** to empower patients and clinicians to make choices driven by patient's personal values. A systematic literature review looking for existing tools and approaches and work completed with patient focus groups has informed this [21]. This study will seek family members input into how best to involve them in this process of priority setting.

3. **Collaboration.** The pathway supports collaborative review by pharmacists and physician.
4. **Integration of 'pause and monitor'.** Patient priorities, potential medication side effects, eTools, clinical consultation record and pause and monitor template plan are integrated in a web-based clinical pathway. This has been piloted with clinicians using a small number of patients in the LTC facilities.

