Adverse effects will be addressed within the usual care clinical setting. Clinical follow-up will be determined according to the particular drugs discontinued and recorded in the web-based clinical pathway.

Frailty Measure

A validated measure of frailty (Edmonton Frail Scale) will be assessed at baseline and 6-months to determine signals of effectiveness of TAPER compared to usual care. We saw signals of improvements following reduction in polypharmacy with a statistically significant difference in the frailty measure, even in our small pilot sample in LTC [20]

See Table 1 for a full list of outcomes, timing of data collection and analysis.

Management

We have partnered with 2 LTC facilities in Brampton, Ontario, each supported by in-house primary care clinicians and pharmacists. We have an excellent working relationship with these facilities after our pilot study. The Medical Director is a co-investigator and key liaison. DM will manage the operation of the study. Regular team meetings with the McMaster research team, Medical Director (JV) and involved staff, training pharmacists to review progress will occur. Research staff will help to ensure fidelity of data collection, with double data entry among a random sample to test accuracy. Randomization and statistical analysis will be carried out by the Biostatistics Unit at St Joseph's Healthcare Hamilton (LT).

3.5: Research Outcomes, Deliverables and Milestones

- *Describe all milestones and anticipated deliverables, outputs and outcomes for the duration of the project.*
- *Provide a project schedule with dates for all milestones and anticipated deliverables, outputs and outcomes for the duration of the project, including all knowledge translation activities.*

Note: The project schedule is mandatory and will be used to track progress of the study.

- *Describe how this project will be managed and deliverables tracked.*

Demographic information such as age, sex, gender, date of birth, and ethnicity will be self-reported in the baseline data collection session in order to describe the sample.

Feasibility Measures (Research Question 2)

Feasibility measures will be assessed using recommendations of Thabane et al. (2010) [22]. Process, resources, management, and scientific areas of feasibility will be assessed through research team and administrative records for the study, and will include:

1. Long-term care recruitment rate
2. Participant recruitment, retention, refusal rates

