3. Number of cancelled-scheduled appointments
4. Proportion meeting eligibility criteria from lists generated by administrative personnel (>70 years and 5+ medications)
5. Proportion needing substitute decision maker involvement
6. Time needed for enrolment target of 80 participants

7. Length of time to complete measures
8. Performance of measures, looking for floor and ceiling effects and change over time
9. Research team's description of appropriateness of the collection surveys and process of data collection
10. Changes to process to meet context demands and needs

Study Measures (Research Questions 1,3,4,5)

Main outcome measures will be collected at baseline and 6-months post-intervention. Additional follow-up by the research team will occur at 1-week, 3-months, and 6-months after initial appointments to facilitate recall and recording of any immediate effects revealed by discontinuation. Study measures include:

1. *Mean number of medications per participant* (primary outcome of interest).
2. *Adverse events* will be collected by solicited enquiry as well as spontaneous patient or clinician report, and serious adverse events reported as a subgroup.
3. *Quality of life* will be measured by the EQ-5D-5L and SF-36 [23]. The EQ5D-5L survey will also be used in our economic analysis [7].
4. *Level of physical functioning impairment* will be measured using the Mantis.
5. *Timed Up and Go* and timed 8-foot walk test will be used as performance measures of physical functioning [24].
6. *Number of falls* (minor and those resulting in injury) will be recorded by self-report and from electronic medical record review.
7. *Pain* will be measured using the Brief Pain Inventory (short-form) [25].
8. *Performance in activities of daily living* (ADL) will be measured using the Barthel Index [26].
9. *Mobility-related fatigue* will be measured by the Avlund Mob-T Scale [27,28].
10. *Sleep* will be measured by a single item on the 15-D quality of life scale [29].
11. *Grip strength* will be assessed using a hand grip dynamometer as per standard testing procedures [30].
12. *Functional ability* will be measured using the Functional Ability Scale for the Elderly [31].
13. *Frailty* will be measured by the Edmonton Frail Scale [32].
14. *Healthcare resource utilization* data will include number of hospitalizations and emergency department and urgent care visits, as well as visits to the family physician.

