15. *Perceived change in side-effects and medication related symptoms* will be self-reported at 1-week, 3-month, and 6-month follow-up.

Semi-structured interview (Research Question 6)

Patients and family members will be asked to participate in a semi-structured interview to explore their experience with deprescribing, and their views on how to incorporate families' perspectives into deprescribing and strategies to address polypharmacy in LTC residents

Data Analysis

Means and standard deviations or proportions will be calculated for demographic information and study outcomes where appropriate. Analysis will involve t-tests or Chi-squared statistics where appropriate. Qualitative data will be analyzed by descriptive methods. See Table 1 for a full list of outcomes, timing of data collection and analysis.

Project Schedule

The project will be carried out over a 16 month period. All research, analysis and KT activities will be carried out in this time period. The project PI and the Research Associate will oversee all activities and will ensure the project schedule is followed (**See Figure 2 for the Project Schedule**)

Section 4 - Project Feasibility

4.1: Feasibility

- Identify all feasibility issues, barriers, challenges and limitations to the successful execution and completion of the study. Specifically address issue related to budget constraints, time constraints, structural issues, and organizational and personnel challenges that may delay or derail timely completion of the study.
- Describe how the investigative team plans on mitigating and overcoming these barriers, challenges and limitations.

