What is the effect of a structured medication discontinuation clinical pathway designed to reduce polypharmacy on mean number of medications and patterns of discontinuation compared to usual practice?	Reduction in mean number of medications	Medication from reconciliation list	Mean number of medications	T ₀ , T ₆	t-test
			Proportion with successful reduction in medication number or dose	T ₆	Chi Square
			Composite variable of mean number of medication discontinuations or dose reductions	T ₆	t-test
What is the effect of a structured medication discontinuation clinical pathway designed to reduce polypharmacy on patient quality of life, frailty, cognition, mobility-related fatigue, nutritional status, physical function capacity, pain, sleep, patient enablement, medication self-efficacy, medication confusion, grip	Improved frailty, disease and treatment burden, quality of life, cognition, fatigue, nutritional status, physical function capacity and ability, pain, sleep, patient enablement, medication self-efficacy and	Frailty	Edmonton Frail Scale	T ₀ , T ₆	t-test
		Disease burden	Bayliss Disease Burden	T ₀ , T ₆	t-test
		Treatment burden	Brief Treatment Burden Scale	T ₀ , T ₆	t-test
		Quality of life	EQ5D-5L (economic analysis)	T ₀ , T ₆	t-test for all Chi squared for proportions
			SF36v2	T ₀ , T ₆	
		Cognition	Mini Mental State Exam	T ₀ , T ₆	

strength, falls and adverse events, and hospital admissions compared to usual practice?
	
lower/fewer falls, healthcare utilization, and adverse events will be reported in the intervention arm compared to the control arm at 6-months
	Fatigue	Avlund Mob-T and Limb-T scale	T ₀ , T ₆	
		Nutritional status	Mini Nutritional Assessment Short-Form	T ₀ , T ₆	
		Physical function capacity and ability	Mänty survey	T ₀ , T ₆	
			Timed up and go	T ₀ , T ₆	
			Global rating of change (balance)	T ₀ , T ₆	
			Grip strength	T ₀ , T ₆	
		Falls	Number	T ₀ , T ₆	
		Pain	Brief Pain Inventory	T ₀ , T ₆	
		Sleep	15-D (sleep item)	T ₀ , T ₆	
		Patient enablement	Patient Enablement Index	T ₀ , T ₆	
		Medication self-efficacy	Self-efficacy for appropriate medication use scale	T ₀ , T ₆	
		Healthcare utilization	Number of hospitalizations	T ₀ , T ₆	
			Number of ED visits	T ₀ , T ₆	
			Urgent care visits	T ₀ , T ₆	
			Proportion of patients with at least one hospitalizati	T ₀ , T ₆	

			on		
		Serious adverse events	Number	T ₀ , T ₆	

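### No side-effect checklist at T0 in both arms and no rule for pre-existing symptoms, so the comparison of non-serious adverse events can be diluted, or biased in either direction

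*Combined protocol and SAP*

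**What the plan says.** Three parts of the plan bear on this.

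- **Section 3.5, Study Measures, item 15.** Side-effects and symptoms linked to medication are rated as perceived change. The rating "will be self-reported at 1-week, 3-month, and 6-month follow-up"; no T0 value is listed.
- **Section 3.5, item 2.** Adverse events "will be collected by solicited enquiry as well as spontaneous patient or clinician report, and serious adverse events reported as a subgroup". No start date, symptom list or definition of a new or worsened event is given.
- **Table 1.** Its hypothesis is that fewer "falls, healthcare utilization, and adverse events will be reported in the intervention arm compared to the control arm at 6-months". Number of serious adverse events is listed at T0 and T6, as are pain, sleep, fatigue, falls, cognition, nutrition and other scales. No visible row covers non-serious events or item 15.

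On timing, section 3.5 says: "Main outcome measures will be collected at baseline and 6-months post-intervention". The extra research contacts take place "at 1-week, 3-months, and 6-months after initial appointments to facilitate recall and recording of any immediate effects revealed by discontinuation". In section 3.4, the TAPER arm has its own record: "Patient priorities, potential medication side effects, eTools, clinical consultation record and pause and monitor template plan are integrated in a web-based clinical pathway". No counterpart is described for usual care before the 6-month outcomes.

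**The concern.** A solicited enquiry finds symptoms whether they are new or old. Residents qualify for this trial by age and number of medications, so many will probably have dizziness, drowsiness, constipation or similar complaints on the day they enter. Without a T0 list, whoever records an event at a later contact has no common reference for deciding whether it is new. The options are to count old symptoms as events or to rely on recall, in a group that the plan expects to include residents with cognitive impairment.

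Adverse events are part of research question 1, and Table 1 states a directional hypothesis about them. Objective 3 in section 3.3 is to test measures for the larger trial, and section 3.4 intends the data for later meta-analysis. A blurred adverse-event contrast would therefore be carried into the planning of the next study. A side-effect measure with no T0 value also cannot be assessed for measured change over time, which is feasibility measure 8.

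**Working it through.** **Inputs from the documents.** Section 3.4 randomises 90 residents 1:1, allowing for 10 dropouts. 90 − 10 = 80, which agrees with the target of 80 in feasibility measure 6 and gives about 40 per arm. The documents give no adverse-event rate, symptom prevalence, alpha or power, so there is no power figure to reproduce.

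**Assumed inputs.** Let *n* be the true risk of a new event, *p* the T0 prevalence of pre-existing symptoms, and *f* the share of old symptoms recognised as old and not counted. New and old symptoms are taken as independent. A two-sided 5% test is assumed for power.

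**Recorded risk.** R = p(1 − f) + [1 − p(1 − f)] × n.

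**Case 1: all old symptoms counted in both arms (f = 0).** The recorded difference is (1 − p) × (true difference).

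| True control v TAPER | p | Recorded control v TAPER | Difference (TAPER − control) |
|---|---|---|---|
| 20% v 10% | 0 | 20% v 10% | −10 points |
| 20% v 10% | 30% | 0.30 + 0.70×0.20 = 44% v 0.30 + 0.70×0.10 = 37% | −7 |
| 20% v 10% | 50% | 0.50 + 0.50×0.20 = 60% v 0.50 + 0.50×0.10 = 55% | −5 |
| 20% v 35% | 0 | 20% v 35% | +15 (power 0.32) |
| 20% v 35% | 20% | 36% v 48% | +12 (power 0.19) |
| 20% v 35% | 40% | 52% v 61% | +9 (power 0.12) |
| 20% v 35% | 60% | 68% v 74% | +6 (power 0.09) |

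In the first block the risk ratio moves from 0.50 to 0.37/0.44 = 0.84 and 0.55/0.60 = 0.92. In the second block TAPER does harm, and dilution hides part of it. Dilution therefore works against finding either benefit or harm.

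**Case 2: recognition differs between arms, with no true effect (n = 30% in both, p = 40%).** The false difference is (1 − n) × p × f.

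- TAPER alone discounts 25%: 0.70 × 0.40 × 0.25 = 7 points in favour of TAPER (58% v 51%).
- TAPER alone discounts 50%: 14 points in favour of TAPER (58% v 44%).
- Control alone discounts 25% or 50%: 7 or 14 points against TAPER.

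With 40 per arm, the standard error for 58% v 44% is √(0.58×0.42/40 + 0.44×0.56/40) = 0.111, about 11 points. These false differences run from below to a little above one standard error.

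**With a complete T0 record used in both arms (f = 1).** R = n in each arm, so the true contrast is recovered: 20% v 35% is again +15 points, and 30% v 30% gives 0.

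**The case against.** The strongest counter-arguments, and what stands of each:

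- **T0 is not empty.** Table 1 gives T0 values for several symptom domains and for serious events, so it would be wrong to infer that no symptoms are recorded at entry. This stands. The gap is limited to side-effects outside those scales and to non-serious events.
- **Perceived change already looks back.** Item 15 is a transition rating, and the plan does not say that it feeds the adverse-event count. This also stands. The weakness of item 15 is recall; the adverse-event argument rests on item 2.
- **A tilt towards TAPER is not shown.** A reader might infer that the TAPER web record lets old symptoms be screened out in that arm only. The documents do not support this. The phrase about potential side effects may mean the known effects of the drugs, and nothing says that the research team uses the pathway to exclude events. Controls also have in-house clinicians and electronic records. The stated aim of capturing effects revealed by discontinuation could equally raise TAPER counts.
- **An adverse event conventionally means something new or worse.** That is so, but without a common T0 record the convention cannot be applied uniformly.
- **A missing row is weak evidence.** Some pages were not available to this review, and visible Table 1 also omits the Barthel Index and the 8-foot walk, which section 3.5 names. A T0 checklist elsewhere cannot be excluded.
- **This is a feasibility trial.** Medication number is the primary signal. This limits the consequence but does not remove it.

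**Conclusion.** The point holds in a limited form. As the visible text stands, pre-existing and new non-serious symptoms cannot be separated on a common basis in the two arms. The adverse-event difference shrinks by the factor 1 − p if all old symptoms are counted: to 70% of its true size at 30% prevalence and to 50% at 50% prevalence. That is an upper bound on the dilution at a given prevalence, because some old symptoms would be recognised as old. If recognition differs between arms, false differences of 7 to 14 points arise in the examples above, in either direction. Such a difference in recognition is plausible because no blinding is described and the follow-up is framed around discontinuation, but the documents do not establish it. Every rate used is an assumption, and the figures show the mechanism rather than a forecast. The primary outcome and the number randomised are unaffected. The change is worth making because it is cheap and T0 status cannot be reliably recovered later.

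**What to change.** Add one solicited side-effect and symptom list to the existing T0 session, asked of every resident before allocation is known. Repeat the same list at the 1-week, 3-month and 6-month contacts in both arms, and state the date from which contacts are counted for usual care, where there is no TAPER appointment.

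Define a non-serious adverse event as a symptom that is new or worse than on the research T0 form, and apply that form, not the clinical pathway record, in both arms. Report change from T0 alongside the perceived-change rating, which can stay as planned. Add a Table 1 row for non-serious events and item 15 with these time points. If a T0 checklist already exists, cite it in section 3.5 and add only the counting rule.

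The cost is choosing or writing a short list, since the plan describes none, and a few more minutes per resident in an already full T0 session. Section 4.1 notes that residents tire and limits testing to a morning slot, so the list should be brief. No extra visit or resident is needed.

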Provide a non-confidential summary in lay terms of the CAT proposal. A lay summary is an overview of a research project described in a way that can be easily understood by those without prior experience of the subject. See Appendix A for CFN's DRAFT - Guidelines for Writing a Lay Summary

Polypharmacy (the use of many medications) is associated with poorer health and drug side effects in older adults. This makes it a concern in long-term care (LTC). We have developed a program (TAPER) for reducing polypharmacy and drug side effects for older adults living in the community. TAPER combines family doctors and clinical pharmacists, with support from the best medical evidence, and patient preferences for treatment. In this study, we will test TAPER in LTC residents. Our focus is whether using TAPER can reverse medication-related mobility problems and prevent falls. We will also explore family members' perspectives on how best to include their views in the TAPER process.

Study participants from two LTC facilities will be put into either an intervention or comparison group at random. We will assess the logistics of the TAPER process in LTC settings as well as patient outcomes including falls, thinking ability, quality of life, mobility, as well as hospitalizations and number of medications. These measures will be collected before and after the program to see if there have been changes for those receiving TAPER compared to a comparison group.

We will use these results to design and gain funding for a much larger research study to test whether this process can improve outcomes for residents when implemented as part of routine care in multiple settings across Canada. We envision a routine preventive system for screening to reduce polypharmacy and side effects in older adults - one that fits alongside immunizations and other screenings.

2.2: Scientific Summary

Provide a non-confidential scientific summary of the CAT proposal, highlighting the hypothesis, study objectives, milestones and deliverables and potential socioeconomic impact. (For funded CAT proposals, this summary will be used externally in media releases, communications and posted on the CFN's website.)

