aiming to focus in more detail on mobility was carried out in the long-term care facilities selected for this application. This has helped us to understand which elements need adjustment for a LTC setting, in particular the need to understand how to involve families in the process. The study proposed in this application will test the robustness of this signal in improvement of specific functional outcomes and provide the basis for scaling up into a large pragmatic randomized controlled trial if there is a signal of reversibility in this feasibility trial.

3.2: Hypothesis and Research Question(s)

- *State the proposed hypothesis and research question(s) to be addressed in the study.*

Hypotheses

We hypothesize that over 6 months, compared to the usual care group, participants in TAPER will have:

1. no change/fewer number of medications (primary signal of interest).
2. no change/improvements in quality of life, level of physical functioning and performance, activities of daily living, fatigue, sleep, functional ability, and number of falls (secondary outcomes).
3. less healthcare resource utilization.

Research Questions

1. What are the effects of TAPER on numbers/doses of medications and adverse events?
2. What signals indicate that impairments of function associated with polypharmacy are reversible?
3. What are the effects on hospitalizations?
4. How can patient priorities and preferences be successfully integrated in the presence of cognitive impairment and family having power of attorney?
5. What are the experiences of patients and their families undergoing 'deprescribing'?
6. What are the key aspects to integrating this model as part of routine practice in long-term care?

3.3: Overall Goal and Objectives

- *Describe the overall goal and specific objectives of the study.*

We wish to build on our work developing and testing the effectiveness of an intervention in primary care to reduce polypharmacy. Our pilot and feasibility studies showed TAPER is suitable for use in routine primary care, scaleable, and demonstrated positive health effects of reducing polypharmacy in community dwelling adults [7]. A pilot study testing a narrow range of medications suggest positive health effects in frail older adults also. Our overall project goal is to adapt, implement and test the TAPER process in LTC. The specific objectives are to:

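### The plan names only an undefined t-test for outcomes measured at baseline and 6 months; adjusting for baseline costs almost nothing and gains from nil to a lot in precision

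*Combined protocol and SAP*

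**What the plan says.** Section 3.5, Study Measures, makes the mean number of medications the primary outcome of interest and states: "Main outcome measures will be collected at baseline and 6-months post-intervention". The Data Analysis paragraph of the same section gives the method: "Analysis will involve t-tests or Chi-squared statistics where appropriate".

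Table 1 lists T0 and T6 for the medication count and the resident-level scales. A t-test is named in the rows for the medication count, frailty, disease burden and treatment burden. The quality-of-life rows carry "t-test for all Chi squared for proportions", and the analysis cells below them are empty. I read that as one merged cell covering the scales underneath; this is an inference from the layout.

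No visible sentence mentions a covariate, regression or analysis of covariance, and none says what the t-test compares. Most of the wording leans towards change:

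- Table 1 labels the medication row "Reduction in mean number of medications".
- The lay summary says measures are "collected before and after the program to see if there have been changes for those receiving TAPER compared to a comparison group".
- Section 3.2 hypothesises "no change/improvements in quality of life".
- The feasibility list in Section 3.5 plans to look at how measures change over time.

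Against that, the Table 1 hypothesis for the secondary outcomes says results "will be reported in the intervention arm compared to the control arm at 6-months", so a comparison of T6 values is not ruled out for the scales.

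**The concern.** Two analysts could follow this plan and report different estimates for the primary outcome, one from T6 values and one from changes. Which is more precise depends on the T0–T6 correlation and on the two SDs, and the documents give none of these. A model that includes the T0 value makes the choice unnecessary and uses data already collected.

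Precision matters here in two ways. Looking for signs of effect is one of the listed objectives (Section 3.3), and the Design paragraph of Section 3.4 expects the trial to inform the sample size of a larger one. A wider interval than necessary blurs the first. Reporting only means and SDs omits the correlation and residual SD that a baseline-adjusted larger trial would be sized on.

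**Working it through.** **Inputs from the documents.** Section 3.4 (Design) randomises 90 residents 1:1 and allows for 10 dropouts: 90 − 10 = 80, or 40 per arm. The feasibility list in Section 3.5 also uses 80 as its enrolment target. No alpha, power, effect size or SD is stated, so there is no power-based figure to reproduce.

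**Assumptions.** The correlation ρ between T0 and T6 is not given; I use 0.3 to 0.9. The SD ratio r = SD(T0)/SD(T6) is not given; I use 1 and 0.8. The documents plan no confidence interval, so the width of a 95% CI serves only as a measure of precision.

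**Formulas.** With SD(T6) = 1 and 40 per arm, half-width = t(0.975, df) × √(2/40) × k.

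- T6-value t-test: k = 1, df = 78.
- Change-score t-test: k = √(1 + r² − 2ρr), df = 78.
- T0-adjusted model: k = √(1 − ρ²) × √(1 + 1/76), df = 77. The second factor is the expected cost of estimating the slope with 80 residents.

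**Example, ρ = 0.7, r = 1.** t(0.975, 78) × √(2/40) = 1.991 × 0.2236 = 0.445, the T6-value half-width. Change scores: k = √0.6 = 0.775, giving 0.345. Adjusted: k = 0.714 × 1.0066 = 0.719, giving 0.320. The saving is 28% against T6 values and 7% against change scores.

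**Results** (half-widths in units of SD(T6)):

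| ρ | T6 values | Change, r = 1 | Adjusted | Saving v T6 values | Saving v change, r = 1 | Saving v change, r = 0.8 |
|---|---|---|---|---|---|---|
| 0.3 | 0.445 | 0.527 | 0.428 | 4.0% | 18.8% | 10.8% |
| 0.5 | 0.445 | 0.445 | 0.388 | 12.8% | 12.8% | 4.9% |
| 0.7 | 0.445 | 0.345 | 0.320 | 28.1% | 7.2% | 0.3% |
| 0.8 | 0.445 | 0.282 | 0.269 | 39.6% | 4.5% | −0.7% |
| 0.9 | 0.445 | 0.199 | 0.195 | 56.1% | 1.9% | 1.9% |

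(The 4.5% at ρ = 0.8 is 4.49% before rounding, hence about 4% elsewhere.) The saving against T6 values does not depend on r.

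**Which SD ratio.** Residents are listed if "aged 70 or older and on 5 or more medications" (Section 3.4). That rule cuts off the lower end of the T0 medication count but not of the T6 count, so for the primary outcome r is likely to be below 1. The value 0.8 shows the direction; it is not an estimate. A ratio of 1.25 would give savings of 29, 24, 20 and 20% against change scores at ρ = 0.3, 0.5, 0.7 and 0.8, but nothing in the documents points that way.

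**Which t-test is better.** Change scores beat T6 values when ρ exceeds r/2, which cannot be settled in advance.

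**Worst case.** 1 + r² − 2ρr exceeds 1 − ρ² by (r − ρ)², which is never negative, and 1 − ρ² is never above 1. So the adjusted model can lose only the slope cost and one degree of freedom: [t(77)/t(78)] × √(1 + 1/76) − 1 = 0.68%. With r = 1 it is narrower than both t-tests for ρ between 0.116 and 0.973.

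**Check.** Simulating 8,000 trials at each of ρ = 0.5, 0.7 and 0.8 (r = 1) gave variance ratios of 0.76, 0.51 and 0.36 against T6 values, and 0.76, 0.86 and 0.92 against change scores. The formulas give 0.76, 0.52 and 0.36, and 0.76, 0.86 and 0.91.

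**Larger trial** (equal SDs, large-sample). At ρ = 0.3, 0.5, 0.7 and 0.8, the adjusted sample size is (1 + ρ)/2 = 65, 75, 85 and 90% of the change-score size, or 1 − ρ² = 91, 75, 51 and 36% of the T6-value size.

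**The case against.** The strongest reply is that little may be gained. The wording favours change scores, and under that reading with equal SDs the saving is 7, 4 and 2% at ρ = 0.7, 0.8 and 0.9. For the primary outcome the entry rule pushes the SD ratio below 1, and at 0.8 the saving is about nil at ρ = 0.7 to 0.8. This stands. A reader who sees the 28 and 40% figures might infer that a large gain is to be expected; those figures need the less likely T6-value reading, and the documents do not support treating them as typical.

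This is also a feasibility trial with no power statement and no decision rule tied to the effect estimate, and none of its listed feasibility measures depends on interval width. That limits the severity. It does not remove the point, since signs of effect and sizing a larger trial are among the stated purposes.

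The correlation and residual SD can be computed later from the collected data whichever test is used. This stands too: a reader might infer that the t-test prevents proper sizing of the next trial, and it does not.

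The Data Analysis wording leaves room for judgement, and Section 3.4 assigns the analysis to a biostatistics unit, which may well adjust for baseline. But the visible text does not say so. Some pages are not available and Table 1 is incomplete as read, so the claim is limited to the visible text.

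Finally, the 0.7% limit is an expectation for well-behaved data with complete pairs, not a guarantee for one dataset. Section 3.4 warns of clustered scores and Section 3.5 plans to look for floor and ceiling effects. The fix therefore includes a residual check.

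**Conclusion.** The point holds as a low-severity, nearly free improvement. In the visible text, a t-test is the only analysis named for the medication count and the resident-level scales, its comparison is undefined, and the T0 value is not used as a covariate. The gain from adjustment runs from nil to large: about 4 to 40% against T6 values, 19 down to 4% against changes with equal SDs, and 11% down to −1% against changes at an SD ratio of 0.8, all for ρ from 0.3 to 0.8. The expected loss is at most about 0.7%. These figures rest on 40 complete T0–T6 pairs per arm, a linear relation, and correlations and SD ratios that I have assumed.

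A reader might infer that the planned t-tests are biased or invalid. They are not: under randomisation both estimate the effect of arm without bias. Nor does this show that the number randomised is wrong.

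**What to change.** In Table 1 and the Data Analysis paragraph of Section 3.5, replace the t-test with a linear model of the T6 value on arm and T0 value. Apply this to the medication count and to each resident-level continuous scale with a T0 value, for example the Edmonton Frail Scale, EQ5D-5L, SF36v2, Mini Mental State Exam, timed up and go, and grip strength. Report the adjusted difference with its 95% CI, the residual SD and the observed T0–T6 correlation.

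Add two short statements: residuals will be checked for scales with skew, floor or ceiling effects, and a simple rule will apply to a resident with a missing T0 value.

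Leave as they are the items measured only at T6, event counts (falls, hospitalisations, visits), single ordinal items (the sleep item and the 5-point Likert items), the global rating of change, which is already a change measure, and the clinician-level items, where there is no randomised arm to compare.

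If the team prefers to keep a t-test, one line should say whether it compares T6 values or changes, and the T0–T6 correlation should still be reported.

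The cost is some wording and one degree of freedom. No extra data, visits or residents are needed.
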